9.7.3 ANALYSIS OF EXPLORATORY EFFICACY ENDPOINTS

9.7.3.1 ANALYSIS OF EXPLORATORY ENDPOINTS RELATED TO NUTRITIONAL STATUS

The following exploratory endpoints related to nutritional status will be analyzed by descriptive statistics using absolute and relative change from baseline:

- Changes from baseline in lean body mass, bone mineral content and fat mass by DEXA scan from baseline to Week 4, Week 24, and Week 48
- Change in body weight from baseline to Week 4, Week 24, and Week 48
- Change in dietary intake of wet weight (oral solid food, oral fluid), energy, macronutrients (fat, carbohydrate, nitrogen, and protein), and electrolytes (sodium, potassium, calcium and magnesium) from baseline to Weeks 4 and 48
- Change in fecal excretion of wet weight (feces), energy, macronutrients (fat, carbohydrate, nitrogen, and protein), and electrolytes (sodium, potassium, calcium and magnesium) from baseline at Weeks 4 and 48

For each MB parameter, it is expected that there will be up to 3 measurements at a given analysis timepoint based on dietary intake and fecal excretion data; hence, the average of all available results over the 72-hour MB period will be used for analysis for each MB parameter at a given analysis timepoint.

p -values and Hodges-Lehmann median estimator along with 95% CI will be produced for change from baseline as defined in the introduction of Section 9.7 for the above specified analysis timepoints.

The body weight will be summarized by descriptive statistics for scheduled visits. If there are multiple body weight results available over MB period, the last available result taken on or prior to the scheduled visit will be used for the corresponding analysis timepoint (Week 4 or Week 48).

9.7.3.2 ANALYSIS OF EXPLORATORY ENDPOINTS RELATED TO EFFICACY

The following exploratory endpoints related to efficacy will be analyzed by descriptive statistics using the absolute change from baseline.

- Change in the total time per day that subjects infuse PS from baseline to every 4 weeks until Week 52 (to be derived based on the total time of PS infusion (including extra fluid) from weekly PS diary data recorded for the corresponding analysis timepoint, divided by 7). *p*-values and Hodges-Lehmann median estimator along with 95% CI will be produced for Week 24 and Week 52 as defined in the introduction of Section 9.7; Note: For handling of missing weekly PS data from diary in case of PS being weaned off, refer to Section 9.3.
- Change in the total time per week that subjects infuse PS from baseline to every 4 weeks until Week 52 (to be derived based on the total time of PS infusion (including extra fluid) from weekly PS diary data recorded for the corresponding analysis timepoint). *p*-values and Hodges-Lehmann median estimator along with 95% CI will be produced for Week 24 and Week 52 as defined in the introduction of Section 9.7; Note: For handling of missing weekly PS data from diary in case of PS being weaned off, refer to Section 9.3.
- Change in electrolytes, minerals, macronutrients and other contents of the PS from baseline to every 4 weeks until Week 52. This is to be derived using each of the following prescription data at the given analysis timepoint. If it is reported that PS is weaned off at a given analysis timepoint, the data will be considered as 0 for analysis.
 - Total energy lipid
 - Total energy glucose
 - Total energy amino acids
 - Magnesium concentration
 - Potassium concentration
 - Sodium concentration

p-values and Hodges-Lehmann median estimator along with 95% CI will be produced for Week 24 and Week 52 as defined in the introduction of Section 9.7.

In addition, for analysis of change in in electrolytes, minerals, macronutrients and other contents of the PS, the relative change from baseline will be also summarized.

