While the patient’s life is saved through PS, the Quality of Life (QoL) of all these patients is impaired by the time they have to spend on the PS infusions as well as the complications derived from the use of PS support, for example, catheter infections, hospitalizations and liver disease. Thus, the main therapeutic goal of SBS-IF treatment is the reduction of the volume of PS across the spectrum in 1) reduction in the time per day on PS, 2) increasing the number of days off PS per week, or 3) the ability to reach full oral/enteral autonomy.

Over time, the remaining intestine goes through a process called intestinal adaptation by which the remaining intestine increases its absorptive capacity to compensate for the reduced length. This post-resection intestinal adaptation is a spontaneous process attempting to ensure a more efficient absorption of nutrients per unit length of the remaining bowel by increasing the absorptive area (structural adaptation) and by slowing the gastrointestinal (GI) transit and/or reducing GI secretions (functional adaptation). This process usually takes place 1–2 years after the resection and

weaning off may occur in 20% to 50% of the patients [Messing, 1999]. Patients are also able to compensate for their malabsorption by increasing oral intake (hyperphagia); however, this ability varies greatly between individual patients [Jeppesen, 2013]. Interestingly, it has been shown that the PS-dependency probability in patients with stoma reaches a plateau very rapidly after surgery, whereas in CIC patients this is reached after almost 2 years, suggesting that intestinal adaptation takes much longer in CIC patients than in stoma patients [Messing, 1999].

It has been demonstrated that this process of intestinal adaptation can be enhanced by administering GLP-2 or more stable analogs with an extended half-life. Endogenous GLP-2 is produced in the enteroendocrine L cell in a nutrient dependent manner and facilitates nutrient absorption by activating pro-absorptive pathways: increasing mesenteric blood flow, inhibiting GI motility and gastric acid secretion, reducing intestinal epithelial permeability, and promoting mucosal growth. Glucagon-like peptide-2 also enhances gut barrier function and induces proliferative and cytoprotective pathways in the small bowel [Brubaker, 2018].

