1.5.2.3 Exploratory Endpoints

Endpoints related to nutritional status

- Changes from baseline in lean body mass, bone mineral content and fat mass by dual-energy X-ray absorptiometry (DEXA) scan from baseline at Weeks 4, 24, and 48
- Change in body weight from baseline at Weeks 4, 24 and 52
- Change in dietary intake of wet weight, energy, macronutrients, fluid and electrolytes (sodium, potassium, calcium, and magnesium) from baseline at Weeks 4 and 48
- Change in fecal excretion of wet weight, energy, macronutrients, fluid and electrolytes (sodium, potassium, calcium, and magnesium) from baseline at Weeks 4 and 48

Endpoints related to efficacy

- Change from baseline in the total time per day that subjects infuse PS at Weeks 24 and 52
- Change from baseline in the total time per week that subjects infuse PS at Weeks 24 and 52
- Change in electrolytes, minerals, macronutrients, and other contents of the PS from baseline at Weeks 24 and 52

Patient reported outcomes

- Short Bowel Syndrome with Intestinal Failure and Colon-in-Continuity - Changes from baseline in Quality of Life Questionnaire (SBS-IF-CIC-QOL) at Weeks 24 and 52
- Short Bowel Syndrome with Intestinal Failure - Changes from baseline in Treatment Impacts - Quality of Life Questionnaire (SBS-IF-TI-QOL) at Weeks 24 and 52

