3.2 Eligibility Criteria

3.2.1 Inclusion Criteria

Initial inclusion criteria (before baseline metabolic balance study)

1. Signed informed consent for this trial prior to any trial specific assessment
2. Male and female subjects with SBS-IF and CIC (at least 28% [\[Cummings, 1973\]](#) and no colostomy), receiving PS, secondary to surgical resection of the small intestine with <200 cm from duodeno-jejunal flexure, based on available medical/surgical records and with the latest intestinal resection leading to SBS-IF being at least 12 months prior to Screening
3. Subject considered stable with regard to PS and weight. Stability is defined as a subject meeting all the following criteria in the 3 months preceding screening:
 - a) Weight change (increase or decrease) ≤5%
 - b) PS volume change not exceeding 25%
 - c) PS energy content change not exceeding 25%
 - d) Actual PS usage in terms of volume and content matches prescribed PS (±10%)
4. Parenteral support requirement of at least 2 days per week as assessed at Screening
5. Willingness to undergo either a colonoscopy or colonography and have any identified polyps removed via colonoscopy
6. Willingness to remain in clinic for metabolic study on three occasions for 5 days
7. Adhere to an individual pre-defined drinking menu and urine measurements during the 48-hour measuring periods
8. No planned restorative surgery or major intestinal surgery (more than 10% intestinal resection or surgery that changes anatomy group, i.e., stoma or CIC), in the trial period
9. Age ≥18 years at Screening
10. Women of childbearing potential must agree to practice effective contraception and to use a highly effective method of contraception during the trial and for 4 weeks after the EOT Visit. Such methods include one of the following: combined (estrogen and progestogen containing) hormonal contraception associated with inhibition of ovulation (oral, intravaginal, transdermal); progestogen-only hormonal contraception associated with inhibition of ovulation (oral, injectable, implantable); intrauterine device; intrauterine hormone-releasing system; bilateral tubal occlusion; or a vasectomized partner. To be considered sterilized or infertile, females must have undergone

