5.1.7 Subject Diaries

Subjects will be asked to complete an e-diary during the screening and treatment period and will receive an electronic device with an app (Medidata Patient Cloud). The e-diary is integrated into the Electronic Data Capture (EDC) system (Section 10.3) and the Investigator will be able to review data that the subject enters.

Subject diary data will be reviewed at the subjects' regular trial visits (Table 1 and Table 2) for all new entries since the last visit. The Investigator must consider re-training of subjects in case of non-compliance with an e-diary entry and/or suspicion of potential mistakes in entry (e.g., PS volume administration very different from prescribed volume).

The following information will be collected:

- For administration of the IMP the following will be documented:
 - Date and time of IMP removal from refrigerator
 - Date and time of IMP preparation (i.e., reconstitution)
 - Volume prepared
 - Vial number used
 - Date and time of injection
 - Who administered the IMP
 - Volume administered (mL)
 - Site of administration
- Body weight (weekly assessment at the subject's home, including an assessment within 2 days before the start of the drinking menu)
- Actual PS volume administered, start date and time of infusion and approximate duration of infusion, will be documented for 7 days prior to each visit (except Visit 3)
- For the 48-hour balance period prior to visits the following will be recorded:
 - Drinking diary: frequency and volume
 - Bristol Stool Form Scale (Section 5.1.7.1)
 - Approximate number of bowel movements
 - Urinary output: frequency and volume
- Following a reduction of PS, the subject will document their body weight and 24-hour urinary volume on 1 day during the time period of 2 to 7 days after the PS volume reduction (Section 5.2.9).

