9.7.2 ANALYSIS OF SECONDARY ENDPOINTS

9.7.2.1 ANALYSIS OF SECONDARY ENDPOINTS RELATED TO PS VOLUME

Subject diary data will be used to obtain PS volume information for analyses. Subjects are to complete diary prior to a scheduled visit. If a subject's e-diary data is not available, PS data recorded at the site will be used for analyses. If a subject has issues/difficulties using the e-diary, PS volume data will be captured in the paper diary and will be entered into the electronic data capture (EDC) system at a trial visit.

The relative as well as absolute change in actual weekly PS volume from baseline to every 4 weeks until Week 52 will be summarized by descriptive statistics. p -values and Hodges-Lehmann median estimator along with 95% CI will be produced for Week 24 and Week 52 as defined in the introduction of Section 9.7. The sum of daily PS volume (including extra fluids) from weekly PS diary data recorded for the corresponding analysis timepoint will be used for analysis.

The proportion (%) of subjects who have achieved a reduction of at least 1 day per week of PS from baseline at every 4 weeks until Week 52 will be produced. Subjects will be considered to

have a reduction of at least one day per week of PS from baseline (incl. extra fluids) if the number of days with PS from weekly PS diary data recorded for the corresponding analysis timepoint is smaller compared to the number of days with PS from weekly PS diary data for the baseline.

In addition, the proportion (%) of clinical responders (20% reduction of PS volume from baseline) at every 4 weeks until Week 52 will be produced. Subjects will be considered to be a clinical responder if the relative change from baseline in weekly PS volume is $\leq -20\%$ for the corresponding visit.

For above analyses, missing weekly PS data from diary (e.g. volume, frequency, etc) will be imputed to 0 in case of PS being weaned off (Refer to Section 9.3.).

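### PS infusion time per day is weekly time divided by 7, so it repeats the weekly endpoint and cannot separate shorter infusion days from fewer infusion days

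*SAP*

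**What the plan says.** Protocol 1.5.2.3 lists two exploratory endpoints on infusion time: "Change from baseline in the total time per day that subjects infuse PS at Weeks 24 and 52" and "Change from baseline in the total time per week that subjects infuse PS at Weeks 24 and 52". Protocol 7.1.3 and SAP 7.3 repeat both.

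SAP 9.7.3.2 gives the derivations. Daily time is the total infusion time, extra fluid included, "from weekly PS diary data recorded for the corresponding analysis timepoint, divided by 7". The weekly endpoint, "Change in the total time per week that subjects infuse PS from baseline to every 4 weeks until Week 52", uses the same diary total undivided. Visits, absolute-change summaries, tests at Weeks 24 and 52, and the rule for weaned subjects are the same for both.

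Protocol 1.1 describes how reduced PS should benefit patients and lists as distinct routes "1) reduction in the time per day on PS, 2) increasing the number of days off PS per week". A third route is full enteral autonomy.

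Two further facts bear on the point. Entry requires "Parenteral support requirement of at least 2 days per week as assessed at Screening", so a subject need not infuse on all seven days. The inputs for a different daily measure also exist. Under Protocol 5.1.7, "Actual PS volume administered, start date and time of infusion and approximate duration of infusion, will be documented for 7 days prior to each visit" (Visit 3 excepted), and SAP 9.7.2.1 already uses the "number of days with PS from weekly PS diary data recorded for the corresponding analysis timepoint" for the endpoint on dropping at least one PS day.

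**The concern.** When two endpoints are listed, a reader expects two pieces of information. Dividing by a fixed 7 gives one result printed in two units. Someone who sees both rows move the same way with the same p-value may take the second as corroboration of the first.

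The label also invites a clinical reading that the number does not support. A fall in time per day suggests shorter infusions. Under this derivation the same fall appears when infusion days are dropped and each remaining one is as long as before. Days off PS have their own endpoint in SAP 9.7.2.1. The length of an infusion day has no summary of its own.

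**Working it through.** **Inputs.** The divisor of 7 and the common diary total come from SAP 9.7.3.2. The methods come from the opening of SAP 9.7: paired t-test, t-based 95% CI, and one-sample Hodges-Lehmann estimate with 95% CI. The minimum of 2 PS days per week comes from Protocol 3.2.1. The documents give no infusion hours, so the hours below are assumptions for illustration.

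**Step 1: duplication.** Let W be the weekly total and D = W/7 at every visit. For each subject, change in D = (change in W)/7.
- t-test: the mean and standard error are both divided by 7, so t and p are unchanged.
- t-based CI: both limits are divided by 7.
- Hodges-Lehmann: every pairwise average is divided by 7, so the estimate and both limits are too.
- Relative change: (change in W/7)/(W0/7) = (change in W)/W0, where W0 is the baseline total, so it is identical.

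A numerical check on simulated subjects (2 to 7 PS days, 8 to 14 h per infusion day at baseline) agreed at n = 8, 9 and 10. At n = 9, both versions gave t = -6.387 and p = 0.00021. The mean change, the Hodges-Lehmann estimate and all CI limits differed by a factor of 7.

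**Step 2: what the daily figure mixes.** Write W = k x h, with k PS days and h hours per infusion day. Then change in D = (k1 x h1 - k0 x h0)/7, where 0 is baseline and 1 is follow-up. It depends on both k and h.

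| Baseline to follow-up | Weekly total (h) | Change in W/7 (h) | Change per infusion day (h) |
|---|---|---|---|
| 5 x 12 h to 4 x 12 h | 60 to 48 | -12/7 = -1.71 | 0 |
| 5 x 12 h to 5 x 9.6 h | 60 to 48 | -12/7 = -1.71 | -2.4 |
| 5 x 12 h to 3 x 14 h | 60 to 42 | -18/7 = -2.57 | +2 |
| 5 x 12 h to 4 x 15 h | 60 to 60 | 0 | +3 |
| 7 x 12 h to 7 x 10 h | 84 to 70 | -14/7 = -2 | -2 |

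The first two rows cannot be told apart by the SAP's measure. In the third it improves while each infusion day lengthens. In these examples the two measures agree only where PS runs on all seven days at both visits.

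**Step 3: fixed number of days.** If k does not change, change in D = (k/7) x change in h. At the entry minimum of 2 days, one hour saved per infusion day appears as 2/7 = 0.29 h.

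**The case against.** The best defence is that an average over calendar days is a fair reading of the protocol's phrase. The endpoint does not say per infusion day, and the list of goals is background text that does not define it. That stands: dividing by 7 is neither an arithmetic error nor a contradiction of the protocol. On that reading, though, the endpoint is redundant.

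A reader might infer that the measure cannot register shorter infusions at all. The documents do not support this. With the number of PS days fixed it does fall, as the second row of the table shows. The limit is attribution.

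A reader might also infer that time per day on PS goes unmeasured. That too goes too far. SAP 9.7.2.1 analyses reductions in PS days, SAP 9.7 lists PS diary data by subject, and with 9 subjects enrolled the length of an infusion day could be worked out from those listings. What is missing is a separate summary.

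The alternative has weaknesses of its own. It is 0/0 for weaned subjects, and scoring them as 0 would credit the loss of all PS days as shorter infusion days, which is the same mixing again. Fewer but longer infusions look like worsening. A short extra-fluid day can pull the average down. These points call for a fixed rule and for reading the measure beside weekly time. They do not favour keeping the divisor of 7, because total weekly time is retained in any case and the W/7 version carries nothing beyond it.

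**Conclusion.** The point holds as a redundancy and an attribution problem. The redundancy is exact and needs no assumption about the data. The size of the mixing rests on assumed hours and could be anything from nil (seven PS days at both visits) to a change of opposite sign (the 3 x 14 h case).

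The practical weight is small. The endpoint is exploratory, the trial is uncontrolled with a safety primary endpoint under protocol version 4, and no decision rule depends on it. One matter cannot be checked: SAP section 2 says that a note to file of 6 December 2022 supersedes other SAP sections, and its text is not reproduced in the documents.

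**What to change.** In SAP 9.7.3.2, derive time per day as total weekly infusion time divided by the number of diary days with PS at that timepoint, using the count already defined in SAP 9.7.2.1. Both quantities include extra fluids, so numerator and denominator match. Summarise the change in subjects still on PS, and report weaned subjects (zero PS days) as a separate count, not as 0. Keep total time per week unchanged as the measure in which weaned subjects enter as 0.

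The cost is one derivation and one stated rule for zero PS days, with no new data. The downside is that the new summary leaves out weaned subjects, so it describes a group selected by outcome and must be read with weekly time and PS days per week. If the calendar-day average is kept, label it as such and drop its duplicate test. Before making the change, the sponsor should confirm that the note to file does not already alter this derivation.

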5.1.6 Parenteral Support Prescription

The Investigator will record in the source documents and eCRF all relevant data related to the prescribed parenteral support including parenteral nutrition throughout the subject's trial participation from initial screening visit until EOT visit. For subjects who discontinue from the trial prematurely, the Investigator will collect data and complete the eCRF up to the subject's EOT Visit, if the subject consents to the collection of this data.

The PS prescription includes infusion and supplements. Data to be recorded include

- PS name
- PS volume (mL)
- PS composition such as:
 - Energy content (kcal/mL): total energy, energy from lipids, glucose, and amino acids
 - Electrolyte content: sodium, potassium, calcium, and magnesium
 - Supplement content (e.g., added vitamins and trace elements)
- PS days per week, i.e., for which days of the week the particular infusion was prescribed.

At each site visit, the Investigator will review the e-diary data with the subject, and adjust the PS as described in Section 4.5.

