7.2 SECONDARY ENDPOINTS

Efficacy endpoints related to PS volume

- Relative change from baseline in actual weekly PS volume at Weeks 4, 24 and 52
- Absolute change from baseline in actual weekly PS volume at Weeks 24 and 52
- Subjects who achieve a reduction of at least 1 day per week of PS from baseline at Weeks 24 and 52
- Clinical responders (20% reduction of PS volume from baseline) at Weeks 24 and 52
- Subjects reaching enteral autonomy at Weeks 24 and 52
- Energy reduction in the Parenteral Nutrition (PN) from baseline at Weeks 24 and 52

Efficacy endpoint related to nutritional, fluid (wet weight) and electrolyte absorption

- Absolute change in absorption of energy over MB periods from baseline to Week 48 (applicable to the protocol version 4)
- Relative change in absorption of energy over MB periods from baseline at Week 48
- Change in absorption of macronutrients over MB periods from baseline at Week 48

- Absolute change in absorption of energy over MB periods from baseline at Week 4
- Change in absorption of macronutrients over MB periods from baseline at Week 4
- Changes in urine output and urinary electrolytes (sodium, potassium, calcium and magnesium) over MB periods from baseline at Week 4 and at Week 48

Patient reported outcomes (PRO)

- Changes from baseline in [REDACTED] at Weeks 24 and 52
- Patient Global Impression of Change (PGIC) at Weeks 24 and 52
- Changes from baseline in Patient Global Impression of Treatment Satisfaction (PGI-TS) at Weeks 24 and 52
- Changes from baseline in Patient Global Impression of Satisfaction with PS (PGI-SPS) at Week 24 and 52
- Changes from baseline in Patient Global Impression of PS Impact (PGI-PSI) at Week 24 and 52.

PK/PD related endpoints

- Trough plasma concentration
- Plasma citrulline levels

Safety endpoints (applicable to the protocol version 3)

- AESI
- Clinical chemistry, hematology, hemostasis, ADAs, and urine analysis
- AEs

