Moreover, the proportion (%) of subjects with enteral autonomy at every 4 weeks until Week 52 will be produced using eCRF data. Once 'weaned off' is recorded in eCRF at a visit, sites are not asked to repeat this data in the next visit. Hence, for analysis, 'weaned off' data will be carried forward to the next analysis timepoint(s) where applicable based on subjects' visit information until indicated otherwise (i.e. no longer reported as 'weaned off') and enteral autonomy will be identified when there are at least two consecutive wean off records for analysis timepoints (after considering carried forward wean-off records) except for Week 52. For Week 52, enteral autonomy will be identified by 'weaned off' data reported at Week 52 since there is no subsequent/further analysis timepoint.

For PS compliance measure, the percent change in actual weekly PS volume from the prescribed weekly PS volume and the difference in actual days per week of PS from prescribed days per week of PS will be assessed for each post-baseline timepoint as well as for overall using the average per subject. The percent change in actual weekly PS volume from the prescribed weekly PS volume is calculated as $(\text{actual weekly PS volume} - \text{prescribed weekly PS volume}) \times 100$, divided by prescribed weekly PS volume for the corresponding timepoint. The difference in actual days per week of PS from prescribed days per week of PS (day) is calculated as actual days per week of PS minus prescribed days per week of PS.

The energy reduction in the PN from baseline at every 4 weeks until Week 52 will be assessed by descriptive statistics of the absolute and relative change in the total energy prescription data from baseline to analysis timepoints. *p*-values and Hodges-Lehmann median estimator along with 95% CI will be produced for Week 24 and Week 52 as defined in the introduction of Section 9.7. If it is reported that PS is weaned off at the given analysis timepoint, the total energy prescription data will be considered as 0 for analysis.

9.7.2.2 ANALYSIS OF SECONDARY ENDPOINTS RELATED TO NUTRITIONAL, FLUID (WET WEIGHT) AND ELECTROLYTE ABSORPTION

The absolute change in absorption of energy, over MB periods from baseline to Week 48 will be summarized by descriptive statistics.

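### The change in PS electrolytes is derived from prescribed concentration, so a cut in volume or days on the same formula shows 0%; PN energy has no stated unit or weekly total

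*SAP*

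**What the plan says.** The exploratory endpoint is the change in electrolytes, minerals, macronutrients and other contents of the PS (SAP 7.3; Protocol 7.1.3). SAP 9.7.3.2 sets the derivation: "This is to be derived using each of the following prescription data at the given analysis timepoint". Six items follow: energy from lipid, glucose and amino acids, and three electrolyte items, of which the first is "Magnesium concentration" and the others are the same quantity for potassium and sodium. The section adds: "If it is reported that PS is weaned off at a given analysis timepoint, the data will be considered as 0 for analysis". Absolute and relative changes are summarised, with p-values and Hodges-Lehmann estimates with 95% CIs at Weeks 24 and 52.

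Volume is treated differently. SAP 9.7.2.1 uses "The sum of daily PS volume (including extra fluids) from weekly PS diary data recorded for the corresponding analysis timepoint". PN energy, a secondary endpoint in the same section, is the absolute and relative "change in the total energy prescription data from baseline to analysis timepoints", with no unit and no weekly total.

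Protocol 5.1.6 has the volume, composition and days per week of each prescribed infusion recorded. Its energy entry reads "Energy content (kcal/mL): total energy, energy from lipids, glucose, and amino acids". It names four electrolytes, including calcium, without a unit.

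**The concern.** The trial hypothesis (Protocol 1.1) is that apraglutide reduces the need for PS, and it names energy, fluids and electrolytes. The adjustment algorithm in Protocol 2.2 acts on weekly PS volume, and one secondary endpoint is "Subjects who achieve a reduction of at least 1 day per week of PS from baseline at Weeks 24 and 52". PS is therefore expected to fall mainly through less volume or fewer days, and a concentration registers neither. It changes only if the formula changes or the subject is weaned and scored 0. The group summary then mixes values near 0% with values of -100% and mainly tracks the proportion weaned. A reader could conclude that electrolyte needs did not fall in subjects whose weekly electrolyte supply did fall.

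There are two related gaps. Protocol 5.1.3.2 allows type, content and volume to vary from day to day, but no rule says how several concentrations become one value per visit. The SAP list also leaves out calcium without giving a reason.

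**Working it through.** The documents give no figure for this endpoint, so there is nothing to reproduce. The check applies the SAP's change formulas to two versions of the variable.

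**Inputs from the documents**
- SAP 9.1: absolute change = Xi − X0; relative change = 100 × (Xi − X0)/X0.
- SAP 9.7.3.2: concentration is the variable; weaned off = 0.
- SAP 9.7.2.1: a subject is a "clinical responder if the relative change from baseline in weekly PS volume is" -20% or lower.
- Protocol 3.2.1, criterion 4: at least 2 PS days per week at entry.
- SAP 2: 2 + 7 = 9 subjects enrolled.

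**Comparator:** weekly amount = concentration × volume per infusion × infusions per week.

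**One subject, composition unchanged.** Take an assumed baseline of 5 days × 2.0 L at 100 mmol/L sodium, which is 1000 mmol/week. The percentages below do not depend on the assumed concentration.
- Volume cut 20%: 5 × 1.6 × 100 = 800 mmol/week, -20%. Concentration stays at 100: 0%.
- One of five days dropped: 4 × 2.0 × 100 = 800 mmol/week, -20%. Concentration: 0%.
- Weaned: -100% on both.

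Dropping one of d identical infusions changes the weekly amount by -1/d: -1/7 = -14.3%, -1/5 = -20%, -1/2 = -50%. Concentration shows 0% each time.

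**Group of 9, w weaned, the others cut by 20% on the same formula (assumed mix)**
- Mean by concentration = -100w/9.
- Mean by weekly amount = -(100w + 20(9 − w))/9.
- Hodges-Lehmann = median of the 9 × 10/2 = 45 Walsh averages.

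| w | Mean, concentration | Mean, weekly amount | Gap (points) | HL, concentration | HL, weekly amount |
|---|---|---|---|---|---|
| 0 | 0% | -20.0% | 20.0 | 0% | -20% |
| 1 | -11.1% | -28.9% | 17.8 | 0% | -20% |
| 2 | -22.2% | -37.8% | 15.6 | 0% | -20% |
| 3 | -33.3% | -46.7% | 13.3 | -50% | -60% |

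For w = 2, both members are non-weaned in 7 × 8/2 = 28 of the 45 Walsh averages, so the median is still 0% by concentration. For w = 3 that count is 6 × 7/2 = 21, below the 23rd ordered value, and the median moves to the mixed pairs: -50% by concentration and -60% by amount.

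If the non-weaned are cut by 50% instead, the concentration means are unchanged and the weekly-amount means become -50.0%, -55.6%, -61.1% and -66.7%.

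**PN energy.** Take an assumed 1.0 kcal/mL on the same baseline: 10,000 kcal/week, 2,000 kcal per bag.
- Field in kcal/mL: a 20% volume cut or a dropped day shows 0%, while the weekly total falls to 8,000 kcal (-20%).
- Field in kcal per bag: the volume cut shows 1,600 against 2,000 (-20%), but the dropped day shows 0%.
- Field in kcal per week: both show -20%, and there is no problem.

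The SAP does not say which applies.

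**The case against.** The strongest reply is that the endpoint concerns contents and never says amount per week. Protocol 5.1.6 files energy and electrolytes under composition, and the quantity of PS is covered by volume, days, infusion time, responder status and enteral autonomy. On that reading a change in concentration is a legitimate answer. It fails on the SAP's own weaning rule: scoring a weaned subject as 0 makes sense for an amount received, not for the composition of a formula no longer given.

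Several points do stand:
- The eCRF, the table shells and the note to file of 6 December 2022, which overrides the SAP, were not available and may define units or a weekly derivation.
- The energy part is a query. The SAP elsewhere uses a prescribed weekly volume, and its list labels energy as totals and electrolytes as concentrations, so a weekly kcal field is possible.
- The group figures follow from an assumed case mix and do not estimate the error in this trial. With 3 weaned, the Hodges-Lehmann gap narrows to 10 points.
- The trial is small and mostly descriptive, its primary endpoints are safety, and weekly amounts should be recoverable from the planned listings.

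**Conclusion.** The concern holds for electrolytes. As SAP 9.7.3.2 is written, a subject still on PS whose volume or days are cut on the same formula shows exactly 0% change in sodium, potassium and magnesium. The weekly amount falls by 20% for the smallest volume responder, and by 14.3% to 50% for one day dropped. In the illustrated group of 9 the mean understates the fall by 13.3 to 20 points, and with up to 2 weaned the Hodges-Lehmann estimate is 0% instead of -20%. The per-subject result rests on unchanged composition and on reading the SAP's field name literally; the group result also needs the assumed case mix.

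The endpoint is exploratory. Weekly volume, PS days, infusion time, responder status and enteral autonomy are unaffected. For PN energy and its lipid, glucose and amino-acid components, the finding is only that unit, time base and weekly aggregation are missing. The calcium omission is a separate, smaller gap. The change should be made before the final analysis; confidence is medium because of the unseen documents.

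**What to change.** In SAP 9.7.3.2 and 9.7.2.1:
1. Confirm and state the eCRF unit and time base of every prescription field used.
2. Define each content as a weekly amount (mmol/week for electrolytes, kcal/week for energy), summed over all products prescribed that week. Multiply by volume or infusion days only where the recorded unit requires it, so that nothing is counted twice. The sum also settles how differing daily products are combined.
3. Analyse absolute and relative change in these amounts with weaned off = 0, and keep concentrations in the listings.
4. Add calcium, or state why it is left out.

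The cost is SAP wording and one derived variable per content. No new data are needed, because Protocol 5.1.6 already has content, volume and days per week recorded for each infusion.
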